1. PURPOSE OF THE STUDY

Purpose: This feasibility study is designed to inform and ultimately support a grant application for funding for an adequately powered randomized, clinical trial (RCT) of daridorexant to prevent postoperative delirium. In this phase 2 study, we will test the following specific aims:

Aim 1: To demonstrate that we can recruit subjects for a placebo-controlled RCT of daridorexant to prevent postoperative delirium.

Target: We will enroll up to 16 subjects. Our recruitment goal is four subjects per month, for a total of 12 subjects completing the protocol.

Aim 2: To demonstrate that we can deliver study compounds to subjects per our proposed methods, including successful use of the OnCore Enterprise Clinical Trial Management System. *Target*: All doses of study compound will be delivered successfully.

Aim 3: To demonstrate successful capture of preoperative, intraoperative, and postoperative data relevant for analyses during the conduct of this trial.

Target: We aim for 100% data capture, including subject retention through all doses of study compound.

Aim 4: To document all potential adverse events (AEs) and serious adverse events (SAEs). *Target*: All subjects will be evaluated daily after receipt of study compound for AEs and SAEs.

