4. STUDY DESIGN

This double-blind, parallel-group trial will randomize patients having cardiac surgery—either surgical aortic valve replacement (SAVR) or coronary artery bypass graft (CABG) surgery—to oral daridorexant 50 mg or identical-appearing placebo. The primary outcomes are feasibility and safety. Study subjects will provide written informed consent after receiving a complete description of the study. See Figure 1 below for a timeline of study assessments (not to scale).

[figure not shown]

Figure 1 – Timeline of Study Assessments

Abbreviations: 3D-CAM, 3-minute Diagnostic interview for the Confusion Assessment Method; CAGE-AID, CAGE [an acronym for "Cut down, Annoyed, Guilty, Eye-opener"] Adapted to Include Drugs; **POD**, postoperative day; **PON**, postoperative night; **TICS**, Telephone Interview for Cognitive Status *25 mg for subjects on a moderate 3A4 inhibitor (see 4.2 STUDY INTERVENTION below for details)

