8. STUDY PROCEDURES

See Table 5 below for the Schedule of Activities

Table 5 - Schedule of activities

Assessment	Screenin	Baseline	PON 1-3	POD 1-3	POD 3-7
	g	(1 hr)	(with	(15 min)	(15 min)
	(15 min)		bedtime		
			meds)		
Verbal consent	X				
CAGE-AID	X				
Written consent		X			
Demographics		X			
CCI		X			
Medication list		X			
Cognition/function					
TICS	X				
MoCA		Full, v8.1			
Lawton		X			
CDR		X			
WTAR		X			
Delirium					
3D-CAM	X			X	Χ [†]
DRS-R98				X	X [†]
Mental health					
PHQ-9		X			
GAD-7		X			
Sleep-related					
PSQI		X			
ESS		X			
RCSQ				X	X [†]
Medication administration			X		
AEs/SAEs					
Questionnaire		X		X	
Chart review*				X	X [†]
Subject to guess whether they received				POD 3	
daridorexant or placebo	 				

Abbreviations: **3D-CAM**, 3-Minute Diagnostic Interview for Confusion Assessment Method; **CAGE-AID**, CAGE [acronym for "Cut-down, Annoyed, Guilt, Eye-opener"] adapted to include drugs; **CCI**, Charlson comorbidity index; **CDR**, Clinical Dementia Rating; **DISH**, Depression Interview and Structured Hamilton; **DRS-R98**, Delirium Rating Scale, Revised 98; **ESS**, Epworth Sleepiness Scale; **GAD-7**, 7-item Generalized Anxiety Disorder scale; **Lawton**, Lawton Instrumental Activities of Daily Living; **MoCA**, Montreal Cognitive Assessment; **PHQ-9**, 9-item Patient Health Questionnaire; **POD**, postoperative day; **PON**, postoperative night (*i.e*, the night of POD 0 [the day of surgery] is defined as PON 1); **PSQI**, Pittsburgh Sleep Quality Index; **RCSQ**, Richards-Campbell Sleep Questionnaire; **TICS**, Telephone Interview for Cognitive Status; **WTAR**, Wechsler Test of Adult Reading

Screening procedures:

As indicated under **7. CONSENT PROCESS** above, consent will involve two steps—a verbal consent for study eligibility screening and, subsequently, signed consent. When obtaining verbal consent, we will

^{*}For evidence of adverse events, documentation of delirium, potential sleep confounds

[†]Daily assessments for delirium and sleep will continue if the subject is delirious on POD 3, until delirium resolves.

Version date: 2/3/2025

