6.2 Post-Marketing Experience

The following adverse reactions have been identified during post-approval use of QUVIVIQ. Because these reactions are reported voluntarily from a population of uncertain size, it is not always possible to reliably estimate their frequency or establish a causal relationship to drug exposure.

Psychiatric disorders: Nightmares or abnormal dreams

Immune system disorders: Hypersensitivity (including angioedema, rash, urticaria)

Version date: 2/3/2025

Safety assessments:

In this trial, we obtain demographics and baseline assessment of medical morbidity, medications, cognitive status, and self-report sleep & mental health. Obtaining such information does not entail significant foreseeable risk beyond limited risk of psychological distress or questionnaire fatigue. As we will be completing the 9-question Patient Healthcare Questionnaire (PHQ-9), which assesses suicidal ideation, we have developed a safety plan for anyone who answers positively to question 9 on the PHQ-9 (see Steps taken to minimize risk below).

Adverse event definition:

This is an observational study of medically and surgically ill patients undergoing open-heart surgery, and this population—independent of this study—is at significant risk for a range of medical and surgical complications because of their underlying heart disease, open-heart surgery, and care provided during the perioperative period. In this study, we define an adverse event as any symptom, sign, illness, or experience that develops or worsens during the study that is reasonably attributable to the study assessments or receipt of daridorexant.

Serious adverse event:

A serious adverse event is defined as any adverse event resulting in any of the following:

- Sleep paralysis (inability to move or speak when going to sleep or waking up)
- Cataplexy (discrete episode of muscle weakness, typically associated with strong emotion)
- Complex behaviors while asleep that pose danger to the patient or others (e.g., sexually inappropriate acts)
- Angioedema or anaphylactic reaction to daridorexant
- Death/suicide
- Prolongation of existing hospitalization
- Persistent or significant disability or incapacity
- Medical or surgical intervention required to prevent permanent impairment or damage

Recording adverse events:

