Each adverse event—whether observed by the PI or elicited from or volunteered by the subject—will be documented. Each adverse event will include a brief description of the experience, the date of onset, the date of resolution, the duration and type of experience, the severity, the nature of any potential relationship to study assessments, contributing factors, and any action taken with respect to the assessments. Any such adverse event will be reported to the Data and Safety Monitoring Advisory Council (see 16. Data and Safety Monitoring Plan).

Responsibilities for reporting serious adverse events:

The PI will record all serious adverse experiences that occur during the study period in the appropriate source documents and/or adverse events log as applicable. The timeframe for adverse event reporting will begin from the time of study enrollment to the final study assessment on POD 3 (or on a subsequent postoperative day for those with delirium on POD 3).

Steps taken to minimize risk:

We will adhere to the exclusion criteria listed above which will help avoid the recruitment of patients most at risk of side effects and adverse consequences. Patients will be interviewed each day for any side effects and the medical records will be reviewed and the data collected for Aim 4 of this study.

Risks pertaining to clinical assessment:

The risks pertaining to clinical assessment (neuropsychological testing and questionnaires) are anticipated to be no more than minimal. If the patient exhibits any distress or hesitation in answering specific

questions or completing a questionnaire in general, the evaluation will be suspended and the subject asked whether they wish to either take a break, skip a given section, or withdraw from the study. The PI [name] is a board-certified psychiatrist with clinical expertise in mental health evaluation. If he is conducting the assessment, he will use his medical judgment to determine whether to suspend evaluation or skip portions of the interview. If study personnel are conducting the evaluation, they will be instructed to contact [name] to join the interview and conduct additional assessment as necessary to determine whether the interview should be suspended or modified.

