14. PRIVACY AND CONFIDENTIALITY OF SUBJECTS AND RESEARCH DATA

See also Appendix I – University of Rochester Human Subject Research Electronic Data Security Assessment Form

Risks pertaining to confidentiality of data and information storage:

Study data will be collected confidentially from the patient and collateral informant. Patients will be assigned a sequential study identification number, which is used for all study purposes. Data from interviews and self-report questionnaires including consent forms will be recorded in hardcopy. All hardcopies will be permanently stored in a locked filing cabinet at SMH either in the PI's personal office or the office of study personnel. Name, date of birth, and other identifying information will be kept in a separate locked file. All data will be entered into an electronic database (REDCap, described in next paragraph) into a final dataset that will be de-identified and reside on a secure URMC server. Study personnel will have access to research data. In performing analyses, the PI may share de-identified data with any member of the mentorship team for guidance on analyses.

Study data will be collected and managed using Research Electronic Data Capture (REDCap) tools hosted at URMC.¹⁰⁴ REDCap is a secure, web-based application designed to support data capture for research studies, providing 1) an intuitive interface for validated data entry; 2) audit trails for tracking data

manipulation and export procedures; 3) automated export procedures for seamless data downloads to common statistical packages; and 4) procedures for importing data from external sources.

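### Do the feasibility targets for intraoperative data, retention and dose delivery clash with the Protocol's own schedule and withdrawal rules?

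*Protocol*

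**What the plan says.** Section 4 of the Protocol states: "The primary outcomes are feasibility and safety". Section 1 gives the feasibility targets. Aim 3 is "To demonstrate successful capture of preoperative, intraoperative, and postoperative data relevant for analyses", and its target reads "We aim for 100% data capture, including subject retention through all doses of study compound". Aim 2 concerns delivering study compound by the proposed methods, and its target is "All doses of study compound will be delivered successfully".

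Table 5 (Section 8) has columns for screening, baseline, postoperative nights 1–3, and postoperative days 1–3 and 3–7. Its chart-review row is marked only in the two postoperative-day columns, with the footnote "For evidence of adverse events, documentation of delirium, potential sleep confounds". Section 9 says that "the medical records will be reviewed and the data collected for Aim 4 of this study".

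Section 13 says that consented subjects stay in the study and that the team would remove a patient only for a serious adverse event. Section 9, in the plan for breaking the blind, withdraws any subject whose code is broken in a medical emergency. Sections 1 and 4.1 aim for 12 completers, with Section 1 capping enrolment at 16. Section 17 says that Aims 1 to 3 are not suited to formal statistical analysis.

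**The concern.** Feasibility is a primary outcome, and the study exists to support a grant application for a powered trial. Its targets should therefore be ones that the protocol can measure. Three things seemed to stand in the way.

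- **Intraoperative data.** Aim 3 promises them, but Table 5 has no row or time point for them. The sentences elsewhere that describe data collection do not mention them either. Staff following the schedule alone might collect none.
- **Retention.** Section 13 reads as if nobody leaves except after a serious adverse event. Section 9 requires withdrawal after unblinding and offers voluntary withdrawal, and the enrolment plan leaves room for four non-completers.
- **Doses.** Without a stated denominator, a dose not given because of early discharge or withdrawal could be counted as a delivery failure. That would mix a logistical problem with correct conduct.

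At stake would be the credibility of the feasibility summary in the later application.

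**Working it through.** **1. Intraoperative items.** Table 5 as extracted has 22 assessment rows and 5 time columns; 0 of 22 and 0 of 5 are intraoperative. The observation is correct for the visible text. The question is whether the other sentences show that such data will not be collected.

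- "In this trial, we obtain demographics and baseline assessment of medical morbidity, medications, cognitive status, and self-report sleep & mental health" (Section 9) introduces a discussion of questionnaire risk. It also omits the postoperative delirium and sleep ratings, which Table 5 plainly schedules, so it is not a full list.
- "Study data will be collected confidentially from the patient and collateral informant" (Section 14) is a confidentiality statement. Several exclusion criteria in Section 5 rely on the chart, as does Table 5, so this is not a full list of sources.
- The Section 9 sentence on record review concerns risk minimisation, so it naturally names Aim 4. It does not rule out other uses of the record.
- Table 5 is organised mainly around subject contacts, with durations in minutes. Operative-record items need no contact and can be listed in a case report form.
- Figure 1, the assessment timeline, is not shown.

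The supportable statement is that no visible passage names an intraoperative variable. It does not follow that none will be collected.

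**2. Retention and removal.** Section 13 speaks of removal by the team, whereas the voluntary withdrawal in Section 9 is the subject's own choice; these do not conflict. For unblinding, the trigger is an emergency needing immediate care for stabilisation. The serious adverse event list in Section 9 includes a prolonged hospital stay and intervention needed to prevent permanent harm, and most such emergencies would plausibly meet one of these. A gap remains where an emergency meets no listed criterion, or is only possibly attributable to the drug and so falls short of the reasonable attribution that the adverse event definition requires.

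For the enrolment plan, 12/16 = 75%, so 16 − 12 = 4 subjects may fail to complete. Sixteen is a ceiling and 12 a goal. Participation starts at screening, usually one to two weeks before surgery (Section 8), so losses may precede the first dose. The plan therefore does not contradict a target of retention through dosing.

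**3. Doses.** Inputs: 3 doses per subject (Section 4.2); 12 or 16 subjects (Section 1).

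- Scheduled doses: 12 × 3 = 36; 16 × 3 = 48.
- One dose not given: 35/36 = 97.2%; 47/48 = 97.9%.
- One withdrawal after the first dose, so two not given: 34/36 = 94.4%; 46/48 = 95.8%.

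These figures apply only if every scheduled dose is in the denominator. Aim 2 refers to delivery by the proposed methods, and Section 13 describes provision for at most three nights, ending at discharge. Both support counting doses due, and then the same omissions leave 100%. Early discharge should seldom matter: postoperative night 1 is the night of surgery, so the third dose falls on the night of postoperative day 2. Section 8 says discharge is often on day 3 or 4, and Section 13 calls early discharge rare.

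The targets also make sense only as aspirations. With independent doses and an assumed delivery probability p, the chance that all 36 are given is p^36: 0.70 for p = 0.99, 0.48 for 0.98, 0.16 for 0.95 and 0.02 for 0.90. The Protocol states no rate; this range is illustrative.

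**The case for a change.** The best case for a change is that what is collected, and when, belongs in the schedule of activities and is not a matter to leave to an analysis plan. A primary feasibility aim that covers intraoperative data should have a place there. It is true that the visible schedule offers none, and that part of the objection stands. But Aim 3 is itself the commitment, and coordinators working to it would abstract the usual items from the operative record of at most 16 subjects. A list would record what is already intended.

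The second argument is sharper. If the code shows placebo, the event cannot be attributed to daridorexant. Unless it is attributed to study assessments, it is then not an adverse event under Section 9, and so not a serious one, yet the subject is still withdrawn. Section 13 would not have allowed that removal. This also stands: the two passages do not fully agree and must be reconciled in wording. It is a narrow case, and this review takes no position on which rule should govern.

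The third argument is that Section 17 plans no formal analysis for Aims 1 to 3, so the aim text alone must carry the definition of success. This is weaker. The denominator is unstated, but the surrounding text points to doses due, and an analyst would report doses given, doses due and the reason for each omission.

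**Conclusion.** The concern does not call for a change to the plan. Two small observations are accurate: no visible passage names an intraoperative item, and Section 13 on removal does not entirely match Section 9 on withdrawal after unblinding. The first is a gap that analysts and coordinators fill sensibly, because Aim 3 already commits the team to those data. The second is a point of wording with no consequence for design or analysis. The supposed conflict with 12 completers out of 16 falls away, and the dose-counting point comes down to an unstated denominator.

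The effect is small. On the strictest reading, one omitted dose costs 2.8 percentage points (1/36) or 2.1 (1/48), and no go/no-go rule, test or sample size depends on it. This conclusion assumes that intraoperative items are available in the routine operative record, and that neither Figure 1 nor the case report forms, which are not shown, contradict the text. Confidence is moderate for that reason.

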4.1 SUBJECT POPULATION

We will enroll 16 persons scheduled to have SAVR or CABG at SMH, with the goal of having 12 subjects complete the protocol.

Choice of study population:

We propose a cardiac surgery cohort for several reasons. (1) Surgery provides a convenient model for understanding delirium pathophysiology and interventions as it allows for describing the sample at baseline and prospectively evaluating a cohort at elevated risk of delirium. (2) Cardiac surgery is associated with a 25–50% delirium incidence⁶, due in large part to the older mean age of this population. As noted above, we have found 30% delirium incidence after SAVR at our institution. (3) We select a cardiac surgery cohort over a hip repair cohort as the pain associated with hip pathology and the postop surgical site affects sleep positions before and after surgery, which contributes to SWD, thereby introducing a potential confound.

The subjects in this trial do not qualify as vulnerable populations.

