
Plan for breaking the blind for a subject

If a patient has a medical emergency that requires immediate clinical care for stabilization, including angioedema, anaphylaxis, attempted suicide, or any other condition that is considered—in the opinion of the PI or the primary medical team—as potentially attributable to daridorexant, we will contact the IDS pharmacist to identify whether the patient has received daridorexant or placebo. If this occurs, the subject will be withdrawn from the study, and this will be reported to the RSRB and DSMB.

Legal risks such as the risks that would be associated with breach of confidentiality:

As with any study incorporating research into clinical care, there is a small but real risk of unintentional release of HPI. We will make every effort to secure data and study records under double lock/key and encryption in keeping with institutional standards to prevent this from occurring.

Version date: 2/3/2025

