13. SUBJECT WITHDRAWALS

Definition of treatment failure or subject removal criteria:

All consented subjects will be retained in the study, and all primary analyses will be performed per protocol. All daridorexant arm subjects who develop postop delirium represent patients for whom daridorexant failed to prevent delirium. However, we do not expect daridorexant to prevent all delirium, so we would not use the term "treatment failure" to describe incident delirium in these patients. We would remove patients from the study only in the event of serious adverse events.

What happens to subjects when study ends or if a subject's participation in the study ends prematurely:

Patients will be thanked for their participation in the study and will be advised to call the PI with any questions. Study agent—either daridorexant or placebo—is being provided for up to the first three nights after surgery, but we will not be providing this to those who discharge prior to this. Early discharges are not only rare but indicate that the patient is doing so well that they no longer require inpatient level of care, which implies that they would not have delirium at the time.

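### Do the 100% targets for dose delivery and retention, and the sentence that all consented subjects will be retained, need changing?

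*Protocol*

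**What the plan says.** Section 4 states that "The primary outcomes are feasibility and safety". Section 1 gives each aim a target. For Aim 2 it is "All doses of study compound will be delivered successfully", and for Aim 3 it is "We aim for 100% data capture, including subject retention through all doses of study compound". No lower acceptable level and no stop/go rule is attached to either. Section 17 says that the first three aims are not suited to formal statistical analysis and that their data are collected to inform the follow-on trial.

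On numbers, Section 1 allows up to 16 subjects and Section 4.1 plans 16, "with the goal of having 12 subjects complete the protocol". On retention, Section 13 says "All consented subjects will be retained in the study, and all primary analyses will be performed per protocol", and then "We would remove patients from the study only in the event of serious adverse events".

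Other sections describe ways in which doses or subjects may be lost:
- Section 4.2 allows a late dose only if extubation occurs before midnight.
- Section 13 supplies no study drug after early discharge.
- Section 9 says that after emergency unblinding "the subject will be withdrawn from the study".
- Section 9 also says that a distressed subject has the evaluation suspended, with "the subject asked whether they wish to either take a break, skip a given section, or withdraw from the study".
- Section 7 leaves a delirious subject's continued participation to be decided with the help of the study partner or a legal representative.

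**The concern.** There are two separate worries.

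The first is that a target with no tolerance discriminates poorly. If even good delivery usually produces at least one missed dose, missing the target says little about whether delivery was good or poor. The study exists to support a grant application for a larger trial, so an uninformative criterion on a primary outcome would defeat part of its purpose.

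The second is that Section 13 appears to promise complete retention, with removal only for serious adverse events, while the enrolment plan leaves room for four non-completers and Sections 7 and 9 describe other routes out. If the statement were used as a planning assumption or to define who is analysed, the contradiction would matter.

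**Working it through.** **Inputs.** There are 3 doses per subject (Section 4.2) and 12 completers (Sections 1 and 4.1), so 12 × 3 = 36 doses. The protocol gives no per-dose delivery rate. The rates below are assumptions, taken over the range 80% to 99%. There is no power-based sample size to reproduce.

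**Chance of meeting the 100% target.** With independent doses it is p^36. If each subject gets all three doses or none, it is p^12.

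| True rate p | Independent, p^36 | Fully clustered, p^12 |
|---|---|---|
| 99% | 0.696 | 0.886 |
| 97% | 0.334 | 0.694 |
| 95% | 0.158 | 0.540 |

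**What a miss tells you.** Take P(miss at 80%) / P(miss at 95%).
- Independent: (1 − 0.80^36) / (1 − 0.95^36) = 0.9997 / 0.842 = 1.19.
- Clustered: (1 − 0.80^12) / (1 − 0.95^12) = 0.931 / 0.460 = 2.03.

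So a bare miss is weak evidence.

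**What a success tells you.** With independent doses, all 36 would be delivered with probability 0.158 at a true 95% but only 0.0003 at a true 80%. The exact two-sided 95% lower bound after 36/36 is 0.025^(1/36) = 0.903. Meeting the target would therefore be informative.

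**Would a graded threshold do better?** Take at least 33/36, as an illustration only.
- It is met with probability 0.896, 0.51 and 0.052 at true rates of 95%, 90% and 80% (clustered, at least 11/12: 0.882, 0.659 and 0.275).
- The miss ratio becomes 0.948 / 0.104 = 9.1 (clustered 0.725 / 0.118 = 6.1).

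As a yes/no rule it separates 80% from 95% better, but it is close to a coin flip at 90%. The exact 95% interval for an observed 33/36 is 78% to 98%, and that interval is the same whichever target was written down.

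**Retention.** 12/16 = 0.75. Going the other way, 12 / (1 − 0.25) = 16, but the 25% is back-solved and the protocol states no loss rate. Set against the Section 13 sentences:
- *Enrolment plan (Sections 1 and 4.1).* Up to four non-completers are allowed for. Losses before the first dose would be compatible with Aim 3, which concerns retention through the doses, but they would still be losses of consented subjects. The literal mismatch stands.
- *Unblinding (Section 9).* The trigger is a medical emergency thought potentially attributable to the drug. Two of its examples, angioedema and anaphylaxis, are on the protocol's own list of serious adverse events. The wording differs, but the case lies largely within the Section 13 exception.
- *Distress (Section 9) and delirium (Section 7).* These are choices by the subject or a representative. The Section 13 heading concerns removal criteria and the sentence describes what the investigators would do, so a right to leave does not contradict it.
- *Section 13 itself.* Its next heading deals with participation that ends prematurely, so the section already foresees early exit.

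**Delirium as a route out.** At the 25–50% incidence in Section 4.1, with 6 placebo subjects (half of 12), the chance that at least one becomes delirious is 1 − 0.75^6 = 0.822 to 1 − 0.50^6 = 0.984. This is the chance that someone reaches a decision about continuing. It is not a loss rate; the protocol does not say how many would stop.

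**The case for a change.** The strongest case for a change is that Section 17 plans no formal analysis, so the Section 1 targets are the only yardsticks fixed in advance. A tolerance chosen after a dose has been missed would carry little weight in a grant application. Nor does the protocol say whether a dose withheld because of late extubation or early discharge counts against Aim 2. And because Section 13 says primary analyses are per protocol, who counts as retained might affect who is analysed.

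Some of this stands. A miss is weak evidence, and the denominator for delivered doses is not spelled out. But no rule turns a miss into a failed aim. A report giving doses delivered out of doses due, with the reason for each dose not given, is what an analyst would produce in any case, and it resolves the denominator without an amendment. Retention can likewise be shown from enrolment to completion and from first to last dose. A threshold below 100% would have to be chosen by the sponsor with no delivery rate in the document to support it. The per-protocol point has little force for Aims 1 to 3, which have no formal analysis, and rewording the retention sentence would not move anyone into or out of an analysis set.

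**Conclusion.** The concern does not call for a change. The calculations are correct, but they assess a pass/fail rule that the protocol does not contain. The 100% figures are aspirations in a 12-completer feasibility study, and what informs the next trial is the count and its interval (for example 33/36, 78% to 98%), whose precision is set by the sample size. Preferring a graded threshold is a reasonable design view; it does not show the plan to be in error. Its apparent gain (miss ratio 9.1 against 1.2, or 6.1 against 2.0 with full clustering) rests on assumed delivery rates of 80% and 95%.

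What remains is editorial. Taken literally, the Section 13 sentence on retaining all consented subjects is inconsistent with 12 completers from up to 16 enrolled, and its limit on removal is worded differently from the unblinding paragraph in Section 9. These passages should be reconciled when the protocol is next revised. No endpoint, analysis set, sample size or conclusion depends on it.
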